### **6. ADVERSE EVENTS REPORTING**

Note: No adverse events have been attributed to Positron-Emission Tomography (PET) imaging/diagnostic administration of FMISO at the levels described in the Investigators Brochure. Therefore, no adverse events are expected as a result of the intravenous (IV) administration of FMISO for typical PET imaging applications such as tumor hypoxia.

Note: As with many IV administered agents, FMISO could cause an allergic reaction that could potentially pose a threat to life (anaphylaxis). This has not been observed in limited human exposure to date. Reasonable precautions should be taken, consistent with normal radiologic and clinical facility practice. The patient should be monitored until the PET procedure is completed, and trained personnel and emergency equipment should be available per facility standards.

Qualifying Adverse Events (AEs), including Serious Adverse Events (SAEs), as defined herein, will be reported via the FDA Adverse Event Expedited Reporting System (AERS). For the FMISO IND we will report adverse events based on the FDA final rule for IND safety reporting requirements under 21 CFR part 312 published on September 29, 2010 and implemented on March 28, 2011. This investigational study is not a BA or BE study so 21 CFR part 320 is not applicable. Adverse events will also be reported to the UAB IRB according to their requirements.

## 6.a. General Definitions (from 21 CFR 312.32 (a))

**Adverse Event (AE):** An **Adverse Event** is an untoward medical occurrence associated with the use of the drug in humans, whether or not considered drug related. For this study, the drug is FMISO and adverse events would include any events experienced by a study participant during the Adverse Event reporting period defined in **Table 3**, whether or not it was considered to be related to the FMISO. At the conclusion of the imaging study, the imaging technologist will observe the patient and also inquire if they are back to their usual state of health. If a negative answer is received, then the physician will be called to investigate this report as a possible adverse reaction.

### **Adverse Reaction:**

An **Adverse Reaction** is any adverse event caused by a drug. In this study, the drug is FMISO.

**Suspected adverse reaction** means any adverse event for which there is a reasonable possibility that the IND drug caused the adverse event. For the purposes of IND safety reporting, “reasonable possibility” means there is evidence to suggest a causal relationship between the drug and the adverse event. A suspected adverse reaction implies a lesser degree of certainty about causality than adverse reaction, which means any adverse event caused by a drug.

An **adverse event or suspected adverse reaction** is considered “**unexpected**” if it is not listed in the investigator brochure or is not listed at the specificity or severity that has been observed; or, if an investigator brochure is not required or available, is not consistent with the risk information described in the general investigational plan or elsewhere in the current application.

An **adverse event or suspected adverse reaction is considered “serious”** if, in the view of either the investigator or sponsor, it results in any of the following outcomes: Death, a life-threatening adverse event, inpatient hospitalization or prolongation of existing hospitalization, a persistent or significant incapacity or substantial disruption of the ability to conduct normal life functions, or a congenital anomaly/birth defect. Important medical events that may not result in death, be life threatening, or require hospitalization may be considered serious when, based upon appropriate medical judgment, they may jeopardize the patient or subject and may require medical or surgical intervention to prevent one of the outcomes listed in this definition. Examples of such medical events include: allergic bronchospasm requiring intensive treatment in an emergency room or at home, blood dyscrasias or convulsions that do not result in inpatient hospitalization, or the development of drug dependency or drug abuse.

An **adverse event or suspected adverse reaction is considered “life-threatening”** if, in the view of either the investigator or sponsor, its occurrence places the patient or subject at immediate risk of death. It does not include an adverse event or suspected adverse reaction that, had it occurred in a more severe form, might have caused death.

**Investigational Agent:** An investigational agent is any agent held under an Investigational New Drug (IND) application. For purposes of this study, FMISO is the investigational agent.

## 6.b. AE Reporting Requirements

The investigators on this protocol will report any suspected adverse events that occur after FMISO administration and within the specified follow-up period to [name] and they will work together to determine whether there was an adverse event or adverse reaction and the severity of the adverse event or reaction.

All AEs will be followed by the investigators until resolution, stabilization, scientifically and clinically satisfactory explanation as to attribution and etiology is achieved, or until subject is lost to follow up.

## 6.c. CAEPR / ASAE for FMISO

The Comprehensive Adverse Event and Potential Risks list (CAEPR) provides a single list of reported and/or potential adverse events (AE) associated with an agent using a uniform presentation of events by body system. The Agent Specific Adverse Event List (ASAEL) would include the expected adverse events associated with the use of FMISO. At this time, there have been no reported AEs associated with the use of FMISO and so no ASAE are expected as a result of IV injection of FMISO in our study population with the specifications for our drug product. We will continue to update our CAEPR and ASAE lists as this study progresses, including by reviewing the literature and our in-house data safety monitoring. If any are found, we will begin an ASAE list. Any information on reported AEs for FMISO will be provided by the sponsor to all of the investigators on this protocol.

## 6.d. Potential but Unexpected Adverse Events for FMISO

No adverse reactions have been reported for FMISO based on a review of published literature, publicly available reference sources, and adverse drug reporting systems.

Other general risks for PET/CT imaging include:

The injection site may become infected.

The dose might be extravasated into tissues surrounding the vein catheter leading to localized pain / discomfort.

**Radiation risks:** FMISO injection contributes to lifetime radiation accumulation. The smallest dosage for imaging and safe handling are used for these protocols. The organ and total body doses associated with FMISO imaging are comparable to those associated with other widely used clinical nuclear medicine procedures and are presented in Section 2.2g of this protocol. **Table 1.** summarizes the radiation dosimetry for FMISO.

## 6.e. Review of Safety Information.

As required by 21 CFR 312.32(b), the physician investigators will promptly review all information relevant to the safety of the drug. The physician investigators will also be providing much of this information to the local IRB as well for data safety and review monitoring. The review will include determining whether there is a safety event over time and the causality. As there are no expected events, all events that will be monitored will be unexpected. Reporting will be as described in **Table 3.**

**Characterization of the severity of an Adverse Event:** Adverse events will be graded as below.

**Grade:** Grade denotes the severity of the AE. An AE is graded using the following categories:

- **Mild**
- **Moderate**
- **Severe**
- **Life-threatening or disabling**
- **Fatal**

**NOTE:** Severity is graded on the Cancer Therapy Evaluation Program (CTEP) Common Terminology Criteria for Adverse Events (CTCAE) based scale for each adverse event. For example, an abnormal hemoglobin value is graded for severity from 1 to 5 [death] based upon where that value falls on the CTCAE scale of abnormal hemoglobin values. “Severity” is NOT the same as “Seriousness.” All appropriate clinical areas should have access to a copy of the most current CTCAE and a copy of the CTCAE can be downloaded from (<http://ctep.cancer.gov>).

**Attribution of cause:** The physician investigators will determine whether an adverse event was related to a medical treatment or procedure. Definitions taken from our work with CTEP and NIH give the following definitions for “Attribution” that we will adopt for this IND study: Attribution is a clinical determination, by the investigator, as to whether an AE is related to a medical treatment or procedure. Attribution categories are:

- **Definite:** The AE is **clearly related** to a treatment or procedure
- **Probable:** The AE is **likely related** to a treatment or procedure
- **Possible:** The AE **may be related** to a treatment or procedure
- **Unlikely:** The AE is **likely unrelated** to a treatment or procedure
- **Unrelated:** The AE is **clearly not related** to a treatment or procedure
- **NOTE:** Attribution is part of the assessment of an adverse event. Determining that an event is ‘unlikely related’ or ‘unrelated’ to a study agent or procedure does NOT make the event unreportable, or disqualify the event as an AE. As defined above, an AE is reportable as specified herein if it occurred: **“during the Adverse Event reporting period defined in the protocol, or by applicable guidance, regulation, or policy.”**

#### 6.f. Adverse Event Reporting

Expedited AE reporting for this study will be done through the Cancer Consortium IRB and FDA and as required by FDA MedWatch. These requirements are briefly outlined in the table below. **Table 3.**

##### Reporting Requirements.

	Unexpected	Expected
--	-------------------	-----------------

	Adverse Reaction (known or suspected attributable to the use of FMISO)		AE not attributable to FMISO	AE, AR
	Serious including life-threatening (or death)	Nonserious	Life-Threatening or serious or not serious	None are expected for FMISO
Reporting Time Requirement to the FDA	Report to FDA ASAP and within 7 days of discovery of event (section 6.ii.8.7)	Annual Continuation Review submission	Annual Continuation Review submission	Not applicable to FMISO
Reporting Form for the FDA	IND Safety report of potentially serious risk	Annual Reports / Case reports	Annual Reports / Case reports	Not applicable to FMISO
Reporting Time Requirement to the local IRB	Report to IRB ASAP within 10 days of discovery of event (suspected is defined as 50% probability attributable to FMISO study) this also includes any increased risks with the study even without an AE	At continuation review time	At continuation review time	Not applicable to FMISO
Reporting form for the IRB	Expedited Reporting Form for Unanticipated Problems or Noncompliance and Adverse Event Reporting Form	Form for Unanticipated Problems or Noncompliance, Case reports on continuation form, Data Safety Monitoring Reports	Form for Unanticipated Problems or Noncompliance, Case reports on continuation form, Data Safety Monitoring Reports	Not applicable to FMISO

**6.g. Expedited Adverse Reaction Reporting Guidelines**

Life-threatening (or fatal) adverse reactions must be reported within 7 days to the FDA. The FDA should be notified as soon as the adverse reaction is discovered by telephone or fax or email. The instructions and forms are available at <http://www.fda.gov/Safety/MedWatch/HowToReport/default.htm>. The report should be sent ASAP by mail and followed with a follow-up report. Individual IND safety reports to FDA are submitted on the Medwatch FDA Form 3500A as an "IND Safety Report". The form should be sent to The Director, Office of Generic Drugs in the Center for Drug Evaluation and Research at FDA. The address and phone numbers are available at: <http://www.fda.gov/AboutFDA/CentersOffices/CDER/ucm119100.htm>.

All life threatening adverse reactions reports are submitted to the FDA, THE UAB IRB and to all investigators. A copy of the report is kept on file.

## **7. STATISTICAL CONSIDERATIONS**

### **7.1 Study Design/Endpoints**

This is a Phase II study of a PET imaging agent, [F]FMISO, in patients with HCC who will be receiving standard care with TACE, and with radiation. The imaging study will not impact the patient's treatment. The objective of this study is to evaluate the potential of [F]FMISO as a non-invasive indicator of tissue hypoxia in HCC patients to provide tumor imaging data.

The primary endpoint is changes in [F]FMISO parameters (HV and T:Bmax) between baseline and follow-up scans. The regional tissue: blood values will be determined and hypoxic volume of the primary tumor and metastases will be calculated. The number of pixels in the tumor volume with a T/B ratio  $\geq 1.2$ , indicating significant hypoxia, will be determined and converted to milliliter units to measure the HV. In each tumor region, we will also locate the pixel with the maximum T/B ratio and include this variable, T/Bmax, in our analysis. HV evaluates the volume of tumor that has crossed the threshold for hypoxia and T/Bmax depicts the magnitude of hypoxia.

The exploratory endpoints include overall survival (OS), disease free survival (DFS) and response to XRT by RECIST, mRECIST or EASL (because enhancement changes are known to better reflect treatment response than size changes) criteria.

### **7.2 Sample Size/Accrual Rate**

This is a Phase II study in patients with Hepatocellular Carcinoma (HCC). We propose a sample size of 20 patients for this initial clinical trial because of patient recruitment based on low HCC incident from UAB tumor register data. If the results are promising but inconclusive, they will be used to define a larger multi-center trial. We expect to have a full enrollment in 2 years. From the previous study (Rajendran 2006), a significant hypoxia was identified in 58 patients (79%) in head and neck cancer. The mean

FMISO T/Bmax was 1.6 (range 1.0–3.5) and the mean HV was 40.2 mL (range 0–1092). We expect at least 60% hypoxia/uptake (e.g. TB ratio changes from baseline >1.2) will be identified in HCC patients in this study, thus with a size of 20 patients we will be able to have an accurate estimation of patients who will have undertaken of [F] FMISO with ~ 10% error, and produces a two-sided 95% confidence interval with a width equal to 0.448 for each FMISO PET scan. The size will be also able to evaluate pre-post changes of 1.5 effect size for T/Bmax based on the above published data using one group paired t-test with >80% power at 5% alpha level. Due to the nature of exploratory to generate hypothesis data for future study, the intra correlation between FMISO PET scans within the same subject will not considerate in the sample size consideration this time.

### 7.3 Statistical analysis plan

The primary endpoint analysis of changes in [F]FMISO parameters (HV and T:Bmax) between baseline and 2 follow-up scans will be using paired t-test. Proportion of patients with uptake of [F] FMISO will be reported as N and % and exact 95% confidence interval using the method of Clopper-Pearson. Descriptive analysis such as mean, standard deviation at baseline and follow-up will be estimated with two-sided 95% confidence intervals for all [F]FMISO parameters from PET scans. Longitudinal analysis will be also applied to estimate the changes (slope) between baseline to the first treatment of TACE and sequential treatment of Stereotactic Radiotherapy (SBRT) with auto correlation covariance structure to control patients' intra-correlation. When repeat studies are done sequentially over the course of treatment, changes are expected to be substantial.

The exploratory endpoints analysis include using cox regression analysis to correlate [F]FMISO parameters with overall survival and progression free survival; and using logistics regression analysis to associate [F]FMISO parameters with clinical response (yes, no). Baseline [F]FMISO, FU [F]FMISO, and changes of [F]FMISO between baseline and FU will be used individually in order to identify if early image of [F]FMISO at baseline, and treatment with TACE alone (FU1) and with radiation (FU2) can predict survival or response. Survival is defined from the time of initial PET scan to the last follow up. Patient's demographics and other prognosis factors will be adjusted in the model. The set of prognostic variables considered in the analysis include standard clinical measures (age, tumor-node-metastasis status), as well as the PET measurements [HV, and FMISO tissue to blood ratio (T/Bmax)]. Due to the high correlation between HV and T/Bmax, and the resulting issue of multicollinearity, these variables will each considered separately with the other prognostic variables. Hazard ratio and Odds ratio will be estimated along with 95% CI. Log-rank tests will be used to compare Kaplan-Meier survival curves associated with patients above and below the median values for the variables of interest. Survival curves are presented with time measured in months. It is important to notice that patient survival will be evaluated every six month through medical record, therefore the Interval-censored survival analysis will be applied which simply extends the approach used for right-censored observations to left- and interval-censored observations (Sun 2006). The probability of a left-censored time is the probability that the true time is less than or equal to the censoring time. And, the probability of an interval-censored observation is the probability that the true time is less than or equal to the upper bound of the interval minus the probability that the true time is less than or equal to the lower bound of the interval. The SAS procedure NPMLE could be used. In addition, we will estimate the optimal cut point of [F] FMISO level using

ROC analysis based on the optimizations of sensitivity and specificity if there is an association between [F]FMISO level and outcomes. Due to small sample size, this analysis is exploratory in order to identify hypotheses for rigorous evaluation in future studies.

Safety analysis will be descriptive include frequency and proportion of patients have reported AE/SAE, by severity and attribution to study although we don't expect any AE/SAE occurs using the imaging agent based on previous published works.

All analysis will be carried out using statistical analysis software (SAS) v9.4.

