## SCHEMA

This Phase II study will investigate the utility of [ $^{18}\text{F}$ ] FMISO in patients with hepatocellular carcinoma (HCC). This trial is designed to test the hypothesis that PET determined [ $^{18}\text{F}$ ]FMISO uptake will indicate tumor hypoxia in patients with HCC treated with trans-arterial chemo-embolization (TACE). We anticipate that [ $^{18}\text{F}$ ] FMISO PET/CT will advance our understanding of the role of hypoxia in HCC prior to treatment and that this knowledge will help design newer combination therapeutic trials for better treatment outcomes.

Adults with HCC and limited hepatic disease eligible for TACE will be enrolled in the study and imaged according to the following schema: After imaging (FMISO 1 and FMISO 2 in the diagram below), patients will be followed for two years or until disease progression. [ $^{18}\text{F}$ ] FMISO PET/CT provides three parameters, tissue hypoxic volume (HV), maximum tissue to blood uptake ratio ( $T:B_{\text{max}}$ ) and tumor blood flow. Both pre-and post-therapy images will be examined to investigate changes in these parameters during the course of TACE treatment.

The study schema is shown below.

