**Figure 1.**

**Figure 1:** Diagram of patient management and timepoints where the [F] FMISO studies will be done in the course of treatment. FMISO PET #1 will be performed prior to treatment. FMISO PET #2 will be performed 1 month after all TACE procedures (in case multiple TACE procedures are performed) and prior to SBRT, and FMISO PET #3 will be performed 1 month following the end of liver stereotactic radiation therapy. 20 patients will be enrolled in this study.

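### The primary paired t-tests use only patients who have the later scan, with no rule for missing scans, and the 0.448 interval width stated for each scan holds only if all 20 patients are evaluable at that scan

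*Combined protocol and SAP*

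**What the plan says.** Section 3.1.2.b admits patients who are scheduled for TACE plus SBRT. Figure 1 places scan 1 before treatment and scan 2 one month after the last TACE procedure but before SBRT. For the last scan it says: "FMISO PET #3 will be performed 1 month following the end of liver stereotactic radiation therapy. 20 patients will be enrolled in this study".

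Section 7.2 sets the size ("We propose a sample size of 20 patients for this initial clinical trial") and the expected rate ("We expect at least 60% hypoxia/uptake"). It states that this size "produces a two-sided 95% confidence interval with a width equal to 0.448 for each FMISO PET scan". It also claims more than 80% power for an effect size of 1.5 in T/Bmax with a paired t-test.

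Section 7.3 makes the paired t-test the primary analysis of the HV and T/Bmax changes "between baseline and 2 follow-up scans will be using paired t-test". The proportion with uptake gets an "exact 95% confidence interval using the method of Clopper-Pearson". A longitudinal analysis with an autocorrelation covariance structure is added to estimate the changes as a slope. It is not named as primary, and 7.3 does not say whether patients with incomplete scans enter it.

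No section gives an analysis set for the imaging endpoint, a rule for missing scans, a replacement rule or an expected loss. Section 7.4 bases conclusions on all eligible patients, but for treatment response only.

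The Schema mentions two scans where Figure 1 has three: "After imaging (FMISO 1 and FMISO 2 in the diagram below), patients will be followed for two years or until disease progression".

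**The concern.** Aims 1.1.b and 1.1.c will be read side by side: what happens to hypoxia after TACE, and what has happened by the end of SBRT. A paired t-test needs both scans of the pair. A patient who progresses, dies, withdraws or changes treatment between scans 2 and 3 counts in the first change but not in the second. A difference between the two mean changes can then partly reflect who is left.

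The loss need not be unrelated to the measurement. Section 1 postulates hypoxia as a factor in treatment resistance and recurrence. If that is right, patients whose hypoxia rose most after TACE may be less likely to reach scan 3, and the scan-3 mean would be lowered by selection.

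The stated precision raises a separate question. Enrolment is 20 and the width is computed for 20, yet it is promised at every scan.

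**Working it through.** **1. The plan's own width.** Inputs from 7.2 and 7.3: n = 20, expected proportion 0.60 (x = 12), Clopper-Pearson.

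- Lower limit = Beta quantile(0.025; x, n - x + 1) = Beta(0.025; 12, 9) = 0.3605
- Upper limit = Beta quantile(0.975; x + 1, n - x) = Beta(0.975; 13, 8) = 0.8088
- Width = 0.8088 - 0.3605 = 0.4483

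The stated 0.448 is reproduced, and it uses all 20 patients.

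**2. The width with fewer evaluable scans.** Same formula with x = 0.6n. The documents give no loss rate, so the losses are assumed.

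| Evaluable at the scan | Assumed loss | Lower | Upper | Width |
|---|---|---|---|---|
| 20 | 0% | 0.3605 | 0.8088 | 0.448 |
| 18 | 10% | 0.3473 | 0.8188 | 0.47 |
| 16 | 20% | 0.3317 | 0.8302 | 0.50 |
| 14 | 30% | 0.3132 | 0.8436 | 0.53 |

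At 18, 16 and 14 the product 0.6n is not a whole number. With the nearest whole count (11, 10, 8) the widths are 0.470, 0.494 and 0.535, so the pattern is the same.

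**3. The stated power for the change.** Two-sided 5% paired t-test (two-sided is assumed), noncentral t with n - 1 degrees of freedom and noncentrality 1.5 × √n. Power is above 0.9999 with 20 pairs, 0.9993 with 14, 0.83 with 6 and 0.71 with 5. The claim of more than 80% therefore holds down to 6 pairs.

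**4. Selection in the scan-3 change.** Let D2 and D3 be the changes from baseline to scans 2 and 3, each divided by its SD, bivariate normal with correlation ρ. Assume that the probability of lacking scan 3 is logistic in D2 with slope s per SD, the intercept being set to give the chosen loss. Then

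bias of the completer mean of D3 = ρ × E[D2 centred at its mean, given scan 3 done].

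| Loss | Slope s | E[D2 given scan 3] | Bias, ρ = 0.4 | Bias, ρ = 0.6 |
|---|---|---|---|---|
| 10% | 0.7 | -0.067 | -0.03 | -0.04 |
| 10% | 1.5 | -0.122 | -0.05 | -0.07 |
| 20% | 0.7 | -0.130 | -0.05 | -0.08 |
| 20% | 1.5 | -0.227 | -0.09 | -0.14 |
| 30% | 0.7 | -0.192 | -0.08 | -0.11 |
| 30% | 1.5 | -0.327 | -0.13 | -0.20 |

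The range is 0.03 to 0.20 SD of the change. The minus sign comes from assuming that a larger rise at scan 2 makes scan 3 less likely.

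**5. That bias against sampling error.** The 95% half-width for a mean change, in SDs, is t(0.975; n - 1)/√n: 2.093/√20 = 0.47, 2.110/√18 = 0.50, 2.131/√16 = 0.53, 2.160/√14 = 0.58. The largest bias, 0.20 at 30% loss (14 pairs), is 0.20/0.58 = 0.34 of the half-width. At 20% loss (16 pairs) the largest is 0.14/0.53 = 0.26.

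**6. What a model using all scans does.** It adjusts the completer mean of D3 by ρ × (mean D2 in all patients - mean D2 in completers), which cancels the bias in step 4. This result is built into the set-up, because loss was made to depend only on the observed D2. It is not evidence that loss in this trial will behave that way.

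**The case against.** The best defence is that 7.3 already plans a longitudinal analysis of all three time points with within-patient correlation. Fitted by likelihood, it would use incomplete patients. That narrows the gap but does not close it: the analysis is secondary to the t-tests, its treatment of missing scans is unstated, and one slope would not separate the TACE change from the SBRT change.

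Two further points stand. Section 3.2.1 excludes patients with a life expectancy under 12 months, which limits early deaths. Aim 1.1.c concerns tumours treated with TACE and radiotherapy, so a completer analysis answers a legitimate question. For a patient who never had SBRT, a model-based scan-3 value is hypothetical. This is why the paired t-tests should stay beside the model.

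Several stronger readings are tempting, and the documents do not support them:

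- **Both follow-up scans depend on SBRT.** Scan 2 comes before SBRT, so only scan 3 does.
- **The trial lacks the precision or power it claims for the change.** The 0.448 belongs to a proportion. For the change 7.2 promises only power, and that survives heavy loss.
- **Patients will not be replaced.** The documents are silent on this.
- **Selection could make SBRT appear to have reversed the hypoxia.** At most about a third of a confidence half-width does not support that, and the direction rests on the resistance hypothesis.
- **The Schema stops scanning at progression.** Its wording ends follow-up after imaging. Figure 1, aim 1.1.c and 7.3 all include a third assessment.

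**Conclusion.** The point holds as a gap in specification with modest consequences. If any scans are missed, the two primary changes rest on different patients, and the scan-3 change describes those who finished treatment. Under the assumed 10-30% loss, slope of 0.7-1.5 and correlation of 0.4-0.6, the completer mean is off by about 0.03-0.20 SD of the change, against a half-width of about 0.5-0.6 SD. None of these inputs is in the documents, and the upper end needs all the extreme values together.

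The precision statement is conditional: 0.448 applies to a scan only if all 20 patients are evaluable at it, and a single missed scan already makes it wider (0.46 with 19). The widening is slight to moderate over the assumed losses. The trial describes itself as hypothesis-generating, which keeps this a recommended improvement and not a threat to the study.

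**What to change.** **Section 7.3.** Specify the longitudinal analysis as a likelihood-based repeated-measures model with scan (1, 2, 3) as a category, including every patient with a baseline scan. Report both changes from it, with the paired t-tests beside it, labelled as the completer analysis. State that the model assumes missingness depends on observed scans, and that for patients who never had SBRT its scan-3 value is hypothetical. Report how many scans are missing and why, and give the scan 1 to scan 2 change separately for patients with and without scan 3.

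**Section 7.2.** Limit 0.448 to scans with 20 evaluable patients, and give the width for the numbers expected at scans 2 and 3, for example about 0.50 if 16 reach scan 3.

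**Schema and Figure 1.** Reconcile the two scans named in one with the three in the other.

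**Cost.** A little more analysis, a missing-at-random assumption that cannot be tested fully, and a slightly less favourable stated precision. No extra patients are needed.

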#### **2.1.a Role of Hypoxia in tumor proliferation and treatment responses of HCC**

Rapidly proliferating solid tumors are under-perfused at the central zone due to micro-environment changes and abnormal angiogenesis. These hypoxic areas derive oxygen predominately through the process of diffusion, which is often insufficient. Tumor cells surviving within hypoxic zones are therefore capable of anaerobic metabolism or other adaptive survival mechanisms. Preferential proliferation of cells adapted to hypoxia can thus result in increasing volumes of hypoxia within a growing solid tumor. Tumor hypoxia is a known prognostic indicator of response to anticancer treatments. Hypoxic cells are classically more resistant to radiation (RT).

In HCC, hypoxia is a significant contributor of tumor progression and treatment resistance. HIF-1 $\alpha$  levels are significantly elevated in HCC and act as the trigger for a number of down-stream events leading to tumor progression, invasion and metastases. Furthermore, hypoxia induced HIF-1 promotes gene expression that enhances cell survival under hypoxic conditions. In addition, it is also known that RT responses are enhanced in tumors deficient in the function of hypoxia-inducible factor-1. As with many other cancers, treatment planning can be tailored and intensified if tissue markers can be used to identify a patient at higher risk for treatment failure and poor outcome. PET imaging with a hypoxia specific imaging agent (FMISO) will be an effective means of identifying at risk HCC patients, and will provide critical information for combination treatment planning.

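### The exploratory models for change in FMISO omit the baseline value, so if baseline is prognostic the change effect can be attenuated or reversed

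*Combined protocol and SAP*

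**What the plan says.** Section 7.3 relates FMISO parameters to overall and progression-free survival by Cox regression and to clinical response by logistic regression. Three kinds of FMISO predictor are named: the baseline value, the follow-up value (after TACE, and after radiation), and the change. These "between baseline and FU will be used individually in order to identify if early image of" FMISO at each stage predicts outcome. The natural reading is one FMISO term per model.

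The models are adjusted for demographics and prognostic factors. The prognostic set lists age, tumor-node-metastasis status and the PET measurements HV and T/Bmax, without a time point for the PET measurements. The following sentence uses that list only to keep HV and T/Bmax out of the same model. Nothing in 7.3 says that a model for change also contains the baseline value.

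Section 2.1.a states: "Tumor hypoxia is a known prognostic indicator of response to anticancer treatments". Exploratory aim 1.2.a (section 1.2) is to test FMISO uptake before TACE as an independent predictor of outcome. Section 7.3 calls these analyses exploratory, meant to supply hypotheses for later studies.

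**The concern.** A change score is follow-up minus baseline, so it contains the baseline value with a minus sign. Patients with high baseline values tend to show larger falls, if only through regression to the mean. If baseline itself predicts outcome, a model with change alone credits part of that prediction to the change.

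Two misreadings could follow. If only baseline hypoxia matters, a rise in hypoxia can look protective. If both a high baseline and a rise are harmful, the harm of the rise is understated or may change sign. The purpose of these models is to suggest hypotheses for a larger trial, and the direction of an association is the main content of such a hypothesis.

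**Working it through.** **The plan's own figures.** Section 7.3 gives no figure for these models. The figures in 7.2 reproduce: 12 of 20 (the expected 60%) gives a Clopper-Pearson interval of 0.361 to 0.809, width 0.448, as stated. A paired t-test at effect size 1.5 with n = 20 (two-sided 5%) has power above 0.999, consistent with the stated figure of more than 80%. These size the uptake proportion and the paired test, not the outcome models. Only n = 20 is carried forward ("We propose a sample size of 20 patients for this initial clinical trial").

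**Inputs.** From the documents: 20 patients (7.2); two years of follow-up (5.4); two-year survival after TACE of up to 63% (2.1.b), used here as an assumed survival level. Not in the documents, hence assumed: the baseline effect, the scan-to-scan correlation r, and the ratio k of follow-up SD to baseline SD.

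**Step 1, algebra.** Let B be baseline (SD 1), F follow-up (SD k) and C = F − B. Let the true linear predictor be bB·B + bC·C. Then

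- cov(B, C) = rk − 1
- var(C) = 1 + k² − 2rk
- change-only coefficient ≈ bC + bB·(rk − 1)/(1 + k² − 2rk)

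With k = 1 the fraction is (r − 1)/(2 − 2r) = −0.5 for any r below 1, so the change-only coefficient is about bC − 0.5·bB. It is halved when bB = bC, which is the case where only the follow-up level matters because bC·B + bC·(F − B) = bC·F. It is reversed when bB > 2·bC. For other k the fraction varies:

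- k = 0.7: −0.67 to −1.61 as r goes from 0 to 0.9
- k = 1.3: −0.37 to −0.10 as r goes from 0 to 0.7, and +0.49 at r = 0.9

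**Step 2, hazard ratio per SD of change.** Take baseline HR 2 per SD (bB = ln 2 = 0.693) and bC = 0. The change-only HR is about exp(0.693 × corr), with corr = (rk − 1)/√(1 + k² − 2rk).

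- k = 1, r = 0.2, 0.5, 0.8: corr = −0.63, −0.50, −0.32; HR = 0.65, 0.71, 0.80. Simulated Cox fits gave 0.67, 0.71, 0.81, against about 1.0 with baseline in the model.
- k = 0.7, r = 0.2: −0.86/1.10 = −0.78; HR = 0.58.
- k = 1.3, r = 0.8: +0.04/0.78 = +0.05; HR = 1.04.

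The last two are the extremes of the algebra over these k and r. The simulated range was about 0.60 to 1.03.

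**Step 3, large-sample check.** Simulated Cox log-HR per baseline-SD unit of change (N = 3000, k = 1, r = 0.5, 24-month censoring, about half with events):

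| True situation | bB | bC | Change alone | Change + baseline |
|---|---|---|---|---|
| Only follow-up level matters | 0.70 | 0.70 | 0.30 | 0.67 |
| Only baseline matters | 0.70 | 0 | −0.33 | 0.01 |
| Baseline stronger | 1.00 | 0.35 | −0.15 | 0.39 |
| Baseline has no effect | 0 | 0.70 | 0.69 | 0.71 |

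**Step 4, at the trial's size.** With 63% alive at 24 months, 20 × 0.37 = 7.4, so about 8 events; with a 24-month median, about 10. With n = 20, k = 1, r = 0.2 to 0.8 and both effects harmful (HR 2 each), the change-only model had the wrong sign in about 11% to 23% of runs, against 5% to 8% with baseline included. These percentages move by a few points between simulation runs. When baseline has no effect (bC = 0.70, r = 0.5), adding it lowered the chance of a nominally significant change effect from 53% to 38%.

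The simulations are of Cox models. The step 1 algebra applies approximately to the logistic models too.

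**The case against.** **The baseline value might already be included.** The prognostic set names HV and T/Bmax, and one could stretch this to baseline values. But no time point is given and the list is used only to separate the two parameters, so at best the text is silent.

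**A change-only hazard ratio is a valid marginal association.** True: 7.3 speaks only of correlating, associating and predicting, and states no conditional estimand. The figure misleads only when it is read as the effect of change in patients with the same baseline. That is how a change result is likely to be read, but the plan does not claim it.

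**The baseline effect is not established.** This stands. Aim 1.2.a tests it, section 2.1.a speaks of tumor hypoxia in general, and HR 2 per SD is an assumption. The documents also give neither SDs nor correlations, and 7.3 expects substantial changes over treatment, so equal SDs cannot be presumed.

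**At n = 20, bias is exchanged for variance.** Largely so when only baseline matters: the median absolute error of the change log-HR was 0.43, 0.37 and 0.29 unadjusted against 0.38, 0.34 and 0.31 adjusted (r = 0.2, 0.5, 0.8), and some two-term fits did not converge. The gain is clearer when both effects are real.

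**The analysis is labelled exploratory.** That covers imprecision. It does not cover a systematic pull on the sign, but it does limit the weight of the point.

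A reader might infer that the plan cannot tell whether the baseline, post-TACE or post-radiation scan predicts outcome. The documents do not support that: the separate baseline and follow-up models are planned and answer it directly. Nor do they support saying that the change model will show a rise as protective; that needs an assumed baseline effect and variance pattern.

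**Conclusion.** The point holds for the exploratory change models and no further. As written, these models omit the baseline value of the same parameter. If baseline is prognostic, their coefficient carries part of the baseline effect, usually with reversed sign. The size depends on three quantities that the documents do not give: the baseline effect, the SD ratio and the scan correlation. Over the ranges assumed above, a true change HR of 1.0 would appear as anything from about 0.60 to 1.03. With no baseline effect there is no distortion.

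The baseline models, the follow-up models, the primary paired analysis and the sample size are unaffected. This is an inexpensive improvement to a hypothesis-generating analysis and does not threaten the trial's main results.

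**What to change.** Add one sentence to 7.3, for example: *Each Cox or logistic model that contains a change in HV or T/Bmax will also contain the baseline value of that same parameter; estimates and 95% confidence intervals from these models are descriptive.*

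Keep the baseline-only and follow-up-only models; the follow-up-only model is the direct answer to aim 1.2.b. Keep the stated demographic and prognostic adjustment as well. Dropping either to save a coefficient would be a debatable trade and is not needed for this correction.

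The cost is SAP wording; the baseline scan is already collected. The statistical price is one more coefficient in models with about 8 to 10 events (assumed): wider intervals, possible convergence failures, and lower power if baseline turns out to have no effect (53% to 38% in the case simulated).
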